6.5 Procedures for Monitoring Treatment Compliance

The study pharmacist, using study drug accountability documents (IDUR), will record the preparation and administration of each required dose of IM study drug. Any missed dose will be noted in the pharmacy source documents and on the subject's CRF. The Investigator is responsible for compliance with the protocol procedures and for monitoring the subject's compliance with the visit schedule.

6.6 Study Completion and Discontinuation

A subject may refuse test material treatment, or study procedures at any time during the study. Participation is voluntary, and refusal to participate will involve no penalty, or loss of benefits to which the subject is otherwise entitled. Due to the nature of the test material, the subject will be encouraged to maintain contact with the Investigator and report any SAEs experienced for the entire study period.

The Principal Investigator is permitted to discontinue the subject from test material treatment for medical reasons at any time. However the subject will continue to return for protocol specific safety and efficacy assessments visits for the remainder of the total study period (12-month post dose visit).

6.7 Subject Classification

6.7.1 Evaluable Subject

Any subject who receives at least one dose of study drug and has at least one post dose assessment.

6.7.2 Screen failure

Any subject who was consented and entered into the screening process appropriately, but subsequently did not meet the entry criteria in order to be treated. Subjects who fail

CONFIDENTIAL

screening will not be followed for safety or efficacy assessment, and no other study procedures will be performed.

6.7.3 Lost to follow-up

A subject deemed to be lost to follow-up is any subject who received treatment, but who does not complete scheduled study visits. This includes those subjects who withdraw consent and refuse further study participation and all attempts to contact the subject are deemed unsuccessful.

7.0 Assessments and Procedures

7.1 Safety

7.1.1 Medical History

A complete medical history will be obtained at Baseline. All positive and negative findings will be carefully documented on the CRF. Any new finding discovered during the Baseline evaluation will be considered to be part of the medical history and will not be recorded as an adverse event.

7.1.1.1 Peripheral Vascular Intervention History

The Investigator will perform detailed assessment of all past peripheral vascular interventions prior to study enrollment. If the subject has never undergone a peripheral vascular intervention, then the lack of these events will be documented as well. Information will include: date(s) of intervention, type(s) of intervention (e.g., PTA, peripheral bypass, amputation), intervention site (e.g., iliac, femoro-popliteal, infrapopliteal; and patency of most recent intervention prior to study start (including a description of the most recent vascular imaging if available). Effort will be made to obtain sufficient information for each peripheral vascular procedure to confirm the subject's PAD status at Baseline.

7.1.2 Physical Examination

The Investigator will perform a full physical examination at Baseline and at Days 15, 28, 59, 91, 180 and 365. All changes from the Baseline will be documented on the CRF pages at the time of the follow-up physical examination.

7 1 2 1 Assessment of CLI

The lower extremities will be examined specifically for clinical evidence of CLI, such as ischemic rest pain, ischemic ulceration, gangrenous skin changes, or residual open wound(s) from minor amputation.

Subjects will be classified as having ischemic rest pain if the pain required analysis for more than 2 weeks, and includes the following clinical characteristics:

- 1. Persistent or recurrent pain of the distal portion of the leg (usually toes, forefoot or ankle),
- 2. Pain begins or is increased, on elevation of the leg and improved by dependency.

Ischemic ulceration and gangrenous skin changes are equivalent necrotizing processes for the purpose of this study. In the case of residual open wound(s) from minor amputation, these will be considered ulceration(s) for the purposes of this assessment.

The Investigator will assess the number of individual ulcers and/or gangrenous tissue site(s) for location and size. Excess necrotic tissue and eschar will be removed when possible before taking measurements. Photographs of each ulceration/gangrene area will be taken for documentation purposes only. Two photographs of each ulceration/gangrene area will be obtained at each efficacy time point regardless of whether the area still contains the ulcer/gangrene, and regardless of how many doses of test material the subject received. During the monitoring visit, the monitor will retrieve one of the two photographs for each ulceration/gangrene area. The border of all photographs will be labeled with the photograph date, subject's initials, and the subject's study number assignment.

On efficacy assessment visits, the ulceration/gangrene area will be considered completely healed if assessed as having complete skin closure without drainage or dressing requirements. An ulceration/gangrene area that heals but re-appears and is unhealed at the assessment will be considered not healed. If the subject is discontinued from treatment, he/she will continue to be followed for ulceration/gangrene evaluations so that the subject's data can be included in analyses. If the subject is lost to follow-up without a proper ulceration/gangrene evaluation, the subject will be considered not to have healed.

7.1.3 Safety Laboratory Tests

Safety laboratory tests will include hematology, chemistry and urinalysis. A list of the specific safety and other laboratory tests (tumor markers and infection tests) required is provided in Table 7-1.

7.1.4 Retinal Fundoscopy

Proliferative retinopathy is defined as the presence of new proliferating blood vessels (neovascularization) arising from the retina or optic disc and growing on the retinal surface or into the vitreous cavity screened by an acceptable method (e.g. dilated retinal examination and retinal photographs) at Baseline and Day 365. An ophthalmology examination for proliferative retinopathy must be performed by an ophthalmologist. Results from such evaluations performed within 3 months of Baseline will be accepted.

Table 7-1 Study Specific Laboratory Procedures		
Hematology	Chemistry	
Red blood cell (RBC) count	BUN	
Hemoglobin	Bicarbonate	
Hematocrit	Albumin	
Mean corpuscular volume	Creatinine	
Mean corpuscular hemoglobin	Glucose	
Mean corpuscular hemoglobin concentration	Potassium	
White blood cell count	Sodium	
Neutrophils	Chloride	
Lymphocytes	Uric acid	
Monocytes	Calcium	

Table 7-1 Study Specific Laboratory Procedures			
Eosinophils	Phosphorous		
Basophils	Total protein		
Blood smear	Tumor markers		
Platelet count	Prostate specific antigen (PSA)		
Liver Function Tests	Alpha-fetoprotein		
GGT	Cancer antigen 19-9 (CA 19-9)		
ALT	CA125		
AST	Carcinoembryonic antigen (CEA)		
Alkaline phosphatase	Infection tests		
LDH	HIV		
Total bilirubin	HepBSAg		
	HCV		
Endothelial Progenitor Cell Assay (EPC)	HTLV		
	CMV		
	VDRL		

7.1.5 12-Lead ECG

A screening ECG will be obtained at Baseline. All ECG recordings will be printed in duplicate. The site will provide the final interpretation of the Screening ECG.

7.1.6 Local Injection Site Reaction Assessment

Local injection sites reactions will be assessed using the grading defined by the National Cancer Institute's Common Terminology for Adverse Events v3.0. The grading categories are as follows and will be recorded on the CRF:

Adverse Event	Grade 1	Grade 2	Grade 3	Grade 4	Grade 5
Injection site reaction	Pain; itching; erythema	Pain or swelling, with inflammation or phlebitis	Ulceration or necrosis that is severe; operative intervention indicated		
Ulceration		Superficial ulceration <2 cm size; local wound care; medical intervention indicated	Ulceration ≥2 cm size; operative debridement, primary closure or other invasive intervention indicated (e.g. hyperbaric oxygen)	Life- threatening consequences; major invasive intervention indicated (e.g., complete resection, tissue reconstruction, flap, or grafting	Death
Allergic reaction/ hypersensitivity	Transient flushing or rash; drug fever <38°C (<100.4°F)	Rash; flushing; urticaria; dyspnea; drug fever ≥38°C (≥100.4°F	Symptomatic bronchospasm, with or without urticaria; parenteral medications(s) indicated; allergy-related edema/ angioedema; hypotension	Anaphylaxis	Death

7.1.7 Incidence of Adverse Events

All adverse events and serious adverse events will be recorded on the CRF at each visit.

7.1.8 Serum Sickness

Serum sickness is defined as low grade fever, joint pain, lassitude and myalgias within 72 hours of study drug administration. The incidence of serum sickness will be documented on the CRF.

7.1.9 Dose Limiting Toxicity (DLT)

Dose limiting toxicity will be defined as the occurrence of any of the following:

- Acute anaphylaxis including erythema, hives, wheals, wheezing, stridor or respiratory distress
- Temperature >102°F with negative blood cultures within 24 hours of study drug administration
- Evidence for active tissue necrosis at the injection site within two weeks of study drug administration

Dose limiting toxicities will be recorded on the CRF. In the event of a DLT at any dose, 3 additional subjects will be added to the dose cohort in which the toxicity was observed. If no additional DLTs are observed in the 6 subjects in this dose level, it will be considered the Maximum Tolerated Dose (MTD). If a DLT occurs in 2/6 patients, then the preceding dose level will be considered the MTD.

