- Review all prior evaluations and confirm that subject meets all entry criteria
- Vital signs
- Digital photography and measurement of ulcer (if present)
- Clinical laboratory tests (chemistry, hematology, and urinalysis)
- Serum HGF
- Anti-HGF antibody level
- VM202 DNA level
- Hemodynamic assessments (ABI, TBI, Wave Form)
- TcPO₂
- Pain VAS
- Analgesic use
- Concomitant medications
- Adverse Events

If the subject meets all eligibility criteria, the following will be performed:

- Obtain study drug from the pharmacy
- Administer study drug in 8 separate injections as described above

After study drug administration, the subject will remain in a comfortable, supine position for observation for at least 60 minutes prior to being discharged. Any adverse reaction occurring during this period will be documented on the CRF.

Following study drug administration, the following evaluations will be performed:

- Vital signs (immediately after study drug administration and at 15, 30, and 60 minutes post-dose)
- Endothelial progenitor cell assay
- Concomitant medications
- Injection site reaction assessment

Adverse events

The subject is instructed to call the Study Coordinator if any of the following occur after discharge from the clinic:

- Hives
- Fever
- Rash
- Difficulty breathing
- Itching
- Worsening of a leg ulcer
- Redness or flushing at the site of the test dose

If any of the above occurs, the subject will be instructed to call the clinic immediately and seek medical attention either at the clinic or to go to the nearest Emergency Room for immediate treatment and evaluation. No further study drug administration will occur until it is determined if this is a DLT or as directed by the treating physician.

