8.2 Definition of an SAE

For each AE, you must determine if it is a serious adverse event (SAE) according to the following definition.

An SAE is an AE, occurring at any dose, which fulfills one or more of the following criteria:

- An event that results in death.
- An event that is immediately life threatening. This does not include an event that, had it occurred in a more serious form, might have caused death.
- An event that results in persistent or significant disability or incapacity.
- An event that is a congenital abnormality/birth defect
- An event that requires in-subject hospitalization or prolongs an existing
 hospitalization. Complications that occur during hospitalization and do not meet
 at least one of the above criteria for seriousness are AEs, not SAEs.
 Hospitalization means that the subject was formally admitted to the hospital, and
 does not include presentation at an emergency room.
- An event that, though not included in the above list, is an important medical event that may jeopardize the safety of the subject or may require medical or surgical intervention to prevent one of the outcomes listed above.

Medical and scientific judgment will be exercised in deciding whether a case is serious in those situations where important medical events may not be immediately life threatening or result in death, hospitalization, disability or incapacity. These include events that may jeopardize the subject or may require medical or surgical intervention to prevent one or

more outcomes listed in the definition of serious. Such events will usually be considered as serious. Examples of such events are:

- Angioedema not severe enough to require intubation but requiring intravenous hydrocortisone treatment
- Hepatotoxicity caused by paracetamol (acetaminophen) overdose requiring treatment with N-acetylcysteine
- Intensive treatment at the study site, in an emergency room, or at home for allergic bronchospasm
- Blood dyscrasias (e.g., neutropenia or anemia requiring blood transfusion) or convulsions that do not result in hospitalization
- Development of drug dependency or drug abuse (e.g., analgesics).

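### The allergic dose-limiting toxicity has no grade threshold, so a Grade 3 allergic reaction that is not called anaphylaxis is left out of the DLT count

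*Protocol*

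**What the plan says.** Protocol 7.1.9 lists three items, any one of which is a DLT. The allergic item is "Acute anaphylaxis including erythema, hives, wheals, wheezing, stridor or respiratory distress". The fever item has a temperature, a culture condition and a 24-hour window, and the necrosis item has a two-week window. The allergic item has neither a grade nor a time limit beyond the word acute.

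The CTCAE v3.0 table in Protocol 7.1.6 grades the same kinds of event:

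- Grade 1, injection-site row: "Pain; itching; erythema".
- Grade 2, allergic row: includes "Rash; flushing; urticaria; dyspnea".
- Grade 3, allergic row: symptomatic bronchospasm, a need for parenteral medication, and "allergy-related edema/ angioedema; hypotension".
- Grade 4, allergic row: anaphylaxis.

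Section 8.1 grades all adverse events by CTCAE v3.0 but does not link grade to DLT status. Section 8.2 gives, as an example of an event usually considered serious, "Angioedema not severe enough to require intubation but requiring intravenous hydrocortisone treatment".

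Under 7.1.9 a DLT adds three subjects to the cohort, and 2/6 makes the preceding dose the maximum tolerated dose (MTD). SAP section 3 repeats the 3+3 rule without defining a DLT, and SAP Appendix A lists no DLT table.

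**The concern.** The DLT count is the only written trigger for expanding a cohort or naming the MTD. The item that feeds it for allergic reactions rests on a diagnosis that the protocol's own table reserves for Grade 4. A subject could have a Grade 3 reaction that is detected, graded and reported as serious, and still not enter the count. Hypotension shows this well: 6.2.2 takes vital signs immediately after dosing and at 15, 30 and 60 minutes, so it would be found, but no DLT item names it.

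The word including also leaves a second, less natural reading open, in which any listed sign counts by itself. Erythema and hives would then be DLTs at Grade 1 or 2. The main weakness is the omission of Grade 3 reactions; the loose wording is secondary.

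**Working it through.** **The plan's own figure.** Four cohorts of three give 4 × 3 = 12 subjects; one expansion gives 12 + 3 = 15. This reproduces the stated 12-15. The point concerns a definition and disputes no number.

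**Counting one event in the first three subjects.** The inputs are the 7.1.9 item and the 7.1.6 grades. The natural reading requires anaphylaxis. The loose reading counts any listed sign. The last column applies the wording proposed under the fix.

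| Event, not diagnosed as anaphylaxis | Natural | Loose | Proposed |
|---|---|---|---|
| Grade 3 angioedema or hypotension alone | 0/3 | 0/3 | 1/3 |
| Grade 3 bronchospasm with wheezing | 0/3 | 1/3 | 1/3 |
| Stridor or respiratory distress | 0/3 | 1/3 | 1/3 |
| Isolated hives or injection-site erythema | 0/3 | 1/3 | 0/3 |

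The first row is 0/3 on both readings of the current text. Because including is not exhaustive, angioedema or hypotension does count as a feature of a reaction diagnosed as anaphylaxis; the gap is the reaction without that diagnosis.

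**Effect on the rule.** At 0/3 nothing in the DLT rule calls for expansion. At 1/3, Protocol 4.2 (Number of Study Subjects) and 7.1.9 call for three more subjects, which is 3/12 = 25% of the base sample; 4.2 makes this conditional on the DSMC recommending that the trial continue.

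**How often the readings could differ (illustration only).** The documents give no reaction rate. Let p be an assumed proportion of subjects with a Grade 3 allergic reaction not called anaphylaxis, independent between subjects. The chance of at least one among the first three is 1 − (1 − p)³:

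- p = 0.05: 1 − 0.95³ = 0.143
- p = 0.10: 1 − 0.90³ = 0.271
- p = 0.20: 1 − 0.80³ = 0.488

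The chance of exactly one, where the written rule is clear, is 3p(1 − p)² = 0.135, 0.243 and 0.384. I do not carry the calculation to an MTD, because the protocol states no rule for 2/3.

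**Does another section settle it?** Section 6.2.2 stops dosing for certain symptoms until DLT status is decided but gives no criterion for deciding. Section 8.1 supplies grades without a cut-off. Section 9.4 refers to stopping rules in a Guidance Document that was not supplied. No supplied text says whether a Grade 3 allergic reaction counts.

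**The case against.** The strongest reply is that the DLT decision does not rest on one investigator's reading. Sections 4.5 and 6.1.1 speak of a DLT determined after the safety review, 6.1.1 requires written DSMC notice before the next cohort enrols, and 9.4 has the committee review severity and relationship to drug under pre-specified stopping rules. The amendment log says that CTCAE grading was added to 8.1 so that the DSMC could use it in deciding on escalation. A serious angioedema would therefore reach the committee whatever its label. This stands, and it lowers the risk of escalating past a severe reaction. It does not supply the missing criterion: the committee still has to apply the 7.1.9 definition when it counts.

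A second reply is that anaphylaxis governs the phrase, so isolated erythema is not a DLT. I agree that this is the natural reading, but it is also the reading that leaves Grade 3 reactions out. It may be said, too, that 7.1.9 does not cite the 7.1.6 table, so equating its anaphylaxis with Grade 4 is an inference. That is fair. It is, however, the only grading of anaphylaxis the protocol gives.

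A third reply is that a bare Grade 3 cut-off could weaken safety, because the table places dyspnea at Grade 2 and does not list stridor in the allergic row, while the current item names stridor and respiratory distress. This is correct, and it is why the fix adds to the item and does not replace it.

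Two stronger readings are tempting but not supported:

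- A reader might infer from 6.2.2 that minor signs are meant to count, since its call-in list includes "Redness or flushing at the site of the test dose". But the section then says "No further study drug administration will occur until it is determined if this is a DLT". If such signs were DLTs on sight, nothing would remain to be determined. The list also covers symptoms, such as a worsening leg ulcer, that are not DLT items.
- A reader might infer that counting minor signs would take enrolment above 15 or fix the MTD at the lowest dose. The first needs escalation after 1/6, which 6.1.1 allows with DSMC approval; the second needs 1/6 to name the MTD, as 7.1.9 says. Both cannot apply, and that conflict is a separate matter.

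**Conclusion.** The allergic DLT item should be corrected. As written, and read naturally, it leaves Grade 3 allergic reactions out of the count unless they are called anaphylaxis, although the protocol treats at least one of them as typically serious. The size is one count per event: 0/3 where 1/3 would be expected, and therefore no written call for three more subjects. The 14%, 27% and 49% figures only show how often this could arise at assumed rates of 5%, 10% and 20%; they are not estimates for this product.

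The conclusion rests on two assumptions: that anaphylaxis in 7.1.9 means what 7.1.6 grades as anaphylaxis, and that the DSMC Guidance Document does not already define the allergic DLT. If it does, what remains is to bring the protocol into line with it. The documents do not support saying that the trial would escalate unchecked past a severe reaction.

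**What to change.** Keep the current item, state that its listed signs count as part of an acute systemic reaction, and add:

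*or any allergic reaction/hypersensitivity of Grade 3 or higher per the CTCAE v3.0 row in 7.1.6 (symptomatic bronchospasm, allergy-related edema/angioedema, hypotension) judged at least possibly related to study drug; stridor or respiratory distress counts at any grade; isolated injection-site erythema, rash or urticaria without systemic or respiratory signs is recorded and reviewed but is not a DLT.*

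Use the same words on the CRF and in the DSMC Guidance Document, and leave the 6.2.2 hold on dosing unchanged. If dosing is complete, report allergic DLT counts per cohort at Grade 3 or higher and at Grade 4 from the recorded adverse events, which shows whether the MTD conclusion depends on the definition.

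The cost is one amended item and matching text in two other documents, with no extra assessment. The downside is that a cohort with one Grade 3 reaction adds three subjects; one such expansion stays within the planned 12-15.

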After the first subject in each cohort completes day 30 (\pm 2 days), subsequent to day 15 dosing of the other 2 subjects in the same cohort, an interim safety evaluation will be performed with the submission of safety data to the Data Safety Monitoring Committee (DSMC). If the DSMC recommends continuing the study, the next dose cohort will be treated. This process will be repeated between the second and third dose cohort and between the third and fourth dose cohort. All 4 dose cohorts will be followed for one year from the time of the first dose of study drug administration. If a dose limiting toxicity is observed in one subject in any dose group, three additional subjects will be added to the dose cohort in which the toxicity was observed. If no additional DLTs are observed in the 6 subjects in this dose level, it will be considered the Maximum Tolerated Dose (MTD). If a DLT occurs in 2/6 subjects, then the preceding dose level will be considered the MTD.

Structure: Single center

Sample Size: Approximately 12-15 subjects

Study Population: Subjects selected for this study will have critical limb ischemia

that has not responded to standard therapy with symptoms

including pain at rest, and/or ischemic ulcers.

Study Assessments: The following assessments will be performed at screening and / or at designated time points throughout the study:

• Informed Consent

- Physical Exam
- Vital Signs
- Pregnancy Test
- Photograph and measurement of ulcer
- Mammogram
- Collection of concomitant medications
- Collection of medical history
- Assessment of CLI
- Collection of adverse events
- Ankle Brachial Index (ABI)
- Toe Brachial Index (TBI)

- Wave Form Analysis
- Transcutaneous Oxygen Pressure Assessment (TcPO₂)
- High resolution MRA
- Visual Analog Scale (VAS) for pain
- Analgesic usage
- Safety Laboratory Testing (Hematology, Chemistry, Urinalysis)
- Retinal fundoscopy
- 12-lead ECG
- Tumor marker testing (Alpha feto-protein, CEA, PSA [males only], CA19-9 & CA125)
- Infection testing (HIV, Hepatitis B, CMV, HTLV, VDRL)
- HGF levels
- Anti-HGF antibody levels
- VM202 DNA levels
- Endothelial progenitor cell assay
- Chest X-ray or CT scan of the chest (if the subject has a previous history of tobacco use, a CT scan will be performed instead of the chest X-ray)

Rationale:

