Subjects selected for this study will all have critical limb ischemia defined as partial or complete obstruction of a major artery perfusing either the upper or lower extremity that results in pain either at rest or with exertion, numbness, coldness and/or skin ulceration. They may also be a history of prior amputation, dry gangrene or atrophy associated with the above symptoms. Subjects will not be a candidate for either surgical revascularization or angioplasty.

Number of Study Subjects

There will 12-15 subjects selected for participation in this study with 3 subjects treated in each of four (4) study cohorts. There will be an additional 3 patients treated in a cohort if 1/3 subjects experiences a DLT and if the DSMC recommends continuing the trial.

Schedule of Assessments

The schedule of assessments is listed below in Table 4-1.

Table 4-1 Study Procedures Chart	Screen / Baseline		Treatment Period												
		Firs	First Dose Follow-Up Second Dose 2 nd Follow-Up ⁵												
	Day -30 to Day 1	Day 1 pre-dose	Day 1 post-dose	Day 8 (+/- 2days)	Day 15 Pre dose (+/- 3 days)	Day15 Post-dose	Day 16	Day 21 (+/- 3 days)	Day 28 (+/- 3 days)	Day 59 (+/- 7 days)	Day 91 (+/- 7 days)	Day 180 (+/- 10 days)	Day 365 (+/- 10 days)	Unscheduled Visit	Early Termination
Consent Form	X														
Confirm Eligibility		X													
Medical History	X														
Chest X-ray or CT scan of chest ¹	X												X		X
Physical Exam	X				X				X	X	X	X	X	X	X
Vital Signs (HR, BP, Respiratory)	X	X	X	X	X	X	X	X	X	X	X	X	X	X	X
Retinal Fundoscopy	X												X		X
Pregnancy Test	X				X 6										
Photograph and measurement of ulcer	X	X			X				X	X	X	X	X		X
Clinical Lab Tests	X	X			X		X		X	X	X	X	X	X	X
Tumor markers ²	X				X					X		X	X		
Infection tests ³	X									X		X	X		X
Serum HGF		X		X	X			X		X					
anti-HGF antibodies		X			X					X		X		X	X
Blood VM202 DNA		X						X		X^7					
12-lead ECG	X														
High Resolution MRA	X										X	X			X
Hemodynamic Assessment (ABI, TBI,	X	X			X				X	X	X	X	X	X	X
Wave Form)	Λ	Λ			Λ				Λ	Λ	Λ	Λ	Λ	Λ	Λ
Pain VAS	X	X			X				X	X	X	X	X	X	X
Subject Analgesic use	X	X		X	X		X	X	X	X	X	X	X	X	
TcPO ₂	X	X			X				X	X	X	X	X	X	X
Injection site reaction assessment			X	X		X	X	X	X	X					
Mammogram ⁴	X														
Endothelial Progenitor Cell Assay	X		X			X			X	X		X	X	X	X
Concomitant Medications	X	X		X	X		X	X	X	X	X	X	X	X	X
Adverse Events		X	X	X	X	X	X	X	X	X	X	X	X	X	X

CT scan of the chest instead of chest X-ray will be performed if previous tobacco use

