4.5 Treatments

The test product used in this study is VM202, a plasmid DNA-based therapeutic product expressing HGF. The HGF gene, HGF-X7 is a genomic-cDNA hybrid HGF construct (HGF-X), which expresses both isoforms of HGF with high efficiency. VM202 has been developed using pCK DNA which has been safely used in previous human clinical trials with VEGF as the therapeutic vector. The VM202 plasmid, also identified as pCK-HGFX7 with 7377 base pairs, is composed of a HCMV enhancer/promoter, a growth hormone polyadenylation terminator sequence, ColE1 originator, and the Kanamycin resistance gene, on a pCK backbone.

For each of the 4 cohorts a different dose level will be administered as follows:

Cohort I- 2 mg of VM202

Cohort II- 4 mg of VM202

Cohort III-8 mg of VM202

Cohort IV-16 mg of VM202

In the event that a dose limiting toxicity (DLT) is determined after the safety review between Cohort I and Cohort II, between Cohort II and Cohort III or between Cohort III and Cohort IV, there will be 3 additional subjects treated at the same dose. If a DLT occurs in 2/6 patients, then the preceding dose level will be considered the MTD.

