There will be a mandatory review of all safety data between the treatments of all dose cohorts (Cohorts I-IV). No subject may be enrolled in subsequent cohorts until the DSMC has reviewed the data and provided a written notice to the sponsor that the trial may continue.

In the event that a DLT is determined after the safety review in any cohort, there will be 3 additional subjects treated at the same dose level. If no further DLTs are observed in the 6 subjects and the DSMC approves dose escalation, then subjects can be enrolled to the

next higher dose level. If 2/6 subjects experience a DLT then the preceding dose level will be considered the MTD.

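### After one DLT in six subjects below 16 mg, Protocol 7.1.9, the Synopsis and SAP 3 name that dose the MTD, while Protocol 6.1.1 permits escalation

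*Protocol*

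**What the plan says.** **Result of 1/6.** Protocol 7.1.9 says: "If no additional DLTs are observed in the 6 subjects in this dose level, it will be considered the Maximum Tolerated Dose (MTD"). The Synopsis (Study Design) and SAP Section 3 say the same. Protocol 6.1.1 gives a different consequence for the same result: "If no further DLTs are observed in the 6 subjects and the DSMC approves dose escalation, then subjects can be enrolled" at the next higher dose level.

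**Result of 2/6.** Every section that covers it makes the preceding dose the MTD.

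**Trigger for expansion.** Protocol 7.1.9 says "In the event of a DLT at any dose, 3 additional subjects will be added to the dose cohort". Section 6.1.1 says "In the event that a DLT is determined after the safety review in any cohort, there will be 3 additional subjects treated", and 4.5 opens its rule with "In the event that a dose limiting toxicity (DLT) is determined after the safety review between Cohort I and Cohort II". None of the three gives a count. The Synopsis does: "If a dose limiting toxicity is observed in one subject in any dose group, three additional subjects will be added". SAP Section 3 matches the Synopsis. The paragraph on Number of Study Subjects is the most specific: "an additional 3 patients treated in a cohort if 1/3 subjects experiences a DLT and if the DSMC recommends continuing the trial".

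**Sample size.** The Synopsis gives "Approximately 12-15 subjects". Number of Study Subjects and 4.3 give the same range. Section 9.1 bases it on feasibility.

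**Oversight.** Section 9.4 says the DSMC works under a Guidance Document with stopping rules fixed in advance. Neither the protocol nor the SAP reproduces those rules.

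**The concern.** Safety and tolerability is the primary objective, and this rule decides which dose is called the MTD and who is dosed above it. After 1/6 at 2, 4 or 8 mg, a reader of 7.1.9 reports that dose as the MTD. A reader of 6.1.1 may, with DSMC approval, treat new subjects at double the dose. DSMC approval does not reconcile the two, because the MTD sentence carries no condition. The SAP does not resolve it either: Section 3 repeats one version, and its table list contains no DLT or MTD table.

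The lesser question is what happens when two or three of the first three subjects have a DLT. No section names that result.

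**Working it through.** **Inputs.** Four cohorts of three (Synopsis); expansion by three; stop at two or more DLTs at a dose. No DLT rate is given, so a flat rate p is assumed at every dose, from 1% to 30%. Expansion is taken to follow exactly 1/3.

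**The plan's own figure.** No DLT: 4 x 3 = 12. One expansion, in Cohort IV: 3 x 3 + 6 = 15. So 12-15 is reproduced.

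**Maximum N.**
- If 1/6 ends escalation, an expanded cohort is always the last one, so the maximum is 3 + 3 + 3 + 6 = 15.
- If 1/6 allows escalation, every cohort can expand, so the maximum is 4 x 6 = 24.

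**Probabilities.** For one cohort:
- z = P(0/3) = (1-p)^3
- e = P(1/3) = 3p(1-p)^2
- s = P(1/3, then 0/3) = 3p(1-p)^5
- t = P(2/3 or 3/3) = 3p^2(1-p) + p^3
- f = 1 - z - s, the chance that the cohort fails

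With all four cohorts ahead:
- 1/6 first arises at 2, 4 or 8 mg, after 0/3 in any earlier cohort: s(1 + z + z^2)
- 16 mg is reached: z^3 if 1/6 ends escalation, (z + s)^3 if it allows it
- N > 15: zero if 1/6 ends escalation; otherwise 3sz^2e + 3s^2z + s^3 + s^2(e - s)
- N from 12 to 15: z^3 + z^2e if 1/6 ends escalation; otherwise 1 - P(N > 15) - (f + zf + st + z^2t)

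Worked at p = 10%: z = 0.729, e = 0.243, s = 0.1771, t = 0.028, f = 0.0939.
- 1/6 below 16 mg: 0.1771 x (1 + 0.729 + 0.5314) = 0.400
- 16 mg reached: 0.729^3 = 0.387, against 0.9061^3 = 0.744
- N > 15: 0.0686 + 0.0686 + 0.0056 + 0.0021 = 0.145
- N from 12 to 15: 0.3874 + 0.1291 = 0.517, against 1 - 0.145 - 0.182 = 0.673

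| Assumed DLT rate | 1% | 2% | 5% | 10% | 20% | 30% |
|---|---|---|---|---|---|---|
| 1/6 in a given cohort, % | 2.9 | 5.4 | 12 | 18 | 20 | 15 |
| 1/6 arises at 2, 4 or 8 mg, % | 8.3 | 15 | 30 | 40 | 35 | 22 |
| 16 mg reached, 1/6 ends escalation, % | 91 | 83 | 63 | 39 | 13 | 4.0 |
| 16 mg reached, 1/6 allows escalation, % | 99.6 | 99 | 92 | 74 | 36 | 12 |
| N > 15, 1/6 allows escalation, % | 0.5 | 1.7 | 7.1 | 14 | 13 | 5.7 |
| N from 12 to 15, 1/6 ends escalation, % | 94 | 88 | 73 | 52 | 23 | 9.2 |
| N from 12 to 15, 1/6 allows escalation, % | 99 | 97 | 87 | 67 | 38 | 21 |

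**The 2/3 and 3/3 gap.** At 5%, 10%, 20% and 30%, t = 0.7%, 2.8%, 10.4% and 21.6%. Expanding after such a result would add 3p x t = 0.001, 0.008, 0.06 and 0.19 expected DLTs per cohort. It could not change the MTD, because at least 2/6 is already certain.

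**The case against.** **The planned size shows that 1/6 was meant to end escalation.** A reader might infer this because 15 is the maximum under that rule. The documents do not support it. Under 6.1.1, one expansion at any dose with 0/3 elsewhere also gives 15. Across the assumed rates N falls within 12-15 more often when 1/6 allows escalation. Early stopping can take N below 12 under either rule; for example, 1/6 at 2 mg with escalation ended gives N = 6. The Synopsis also calls the figure approximate. Only the maximum differs.

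**The trigger wording is a second contradiction, so the protocol orders three more subjects after 2/3.** A reader taking 7.1.9 alone might conclude this. Read together, the sections point to one DLT: 6.1.1 and 7.1.9 go on to speak of no further or additional DLTs in the six, and Number of Study Subjects says 1/3. The DSMC stopping rules may cover 2/3 and 3/3. What stands is that the action is not stated in these documents.

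**The probabilities may be too high.** This stands in part. The DLT list in 7.1.9 is narrow, and Section 1.3 reports that a product on the same vector was well tolerated in nine subjects at 2 to 8 mg, which is why 1% and 2% are shown. Appendix E also cites safety shown in the first two cohorts. If only Cohort III remained below 16 mg, the single-cohort row would apply (about 3% to 20%).

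**No section says outright that 1/6 ends escalation.** True; that is inferred from naming the dose the MTD. But enrolling above a dose already declared the maximum tolerated cannot be squared with that declaration. Appendix E describes the rule as clarifying a standard 3+3 design, but the documents do not define that standard, so the label does not settle the matter.

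**Conclusion.** Wrong as written, and it should be fixed. For 1/6 at 2, 4 or 8 mg, current text in 7.1.9, the Synopsis and SAP Section 3 conflicts with current text in 6.1.1. The conflict depends on no assumed rate. Its consequences are a different named MTD, different exposure at higher doses, and a maximum N of 15 or 24.

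How often it would matter does depend on the assumed flat rates: about 8% to 15% at 1% to 2%, and 22% to 40% at 5% to 30%, with all four cohorts ahead. The stated upper limit of 15 is exceeded only under 6.1.1, with probability about 0.5% to 2% at the low rates and 6% to 14% at the higher ones. DSMC review between cohorts is a partial safeguard.

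The missing action after 2/3 or 3/3 is a secondary clarification. It affects exposure and not the choice of MTD, and its expected size is small.

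**What to change.** Use one rule, in the same words, in the Synopsis, Number of Study Subjects, 4.5, 6.1.1, 7.1.9 and SAP Section 3. Settle 1/6 one way, as a decision for the sponsor and the DSMC:

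- **1/6 is the MTD.** Delete the escalation sentence in 6.1.1 and state that escalation ends. The maximum stays at 15 and no subjects are added. The cost is a lower chance of testing 16 mg (39% against 74% at an assumed 10% rate).
- **1/6 allows escalation.** Keep 6.1.1 with DSMC approval, delete the sentence making 1/6 the MTD from the Synopsis, 7.1.9 and SAP Section 3, and restate the maximum sample size as 24. The cost is up to 9 more subjects (24 - 15) and more exposure at higher doses.

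In the same rule, limit expansion to exactly 1/3. State that two or more DLTs at a dose, whenever reached, stop new dosing there and make the preceding dose the MTD; at 2 mg, state that no MTD was established. Check that the DSMC Guidance Document matches. If dosing is already complete, the study report still needs one stated rule for naming the MTD.
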